12.2.2 Procedures for reporting serious adverse events

If an SAE is reported, UCB must be informed within 24 hours of receipt of this information by the site (see contact information for SAE reporting listed in the Serious Adverse Event Reporting section at the front of the protocol). The Investigator must forward to UCB (or its representative) a duly completed “Investigator SAE Report Form for Development Drug” (SAE report form) provided by UCB, even if the data are incomplete, or if it is obvious that more data will be needed in order to draw any conclusions. Information recorded on this form will be entered into the global safety database.

An Investigator SAE report form will be provided to the Investigator. The Investigator SAE Report form must be completed in English.

It is important for the Investigator, when completing the SAE report form, to include the assessment as to a causal relationship between the SAE and the IMP administration. This insight from the Investigator is very important for UCB to consider in assessing the safety of the IMP and in determining whether the SAE requires reporting to the regulatory authorities in an expedited manner.

Additional information (eg, autopsy or laboratory reports) received by the Investigator must be provided within 24 hours. All documents in the local language must be accompanied by a translation in English, or the relevant information included in the same document must be summarized in the Investigator SAE report form.

The Investigator is specifically requested to collect and report to UCB (or its representative) any SAEs (even if the Investigator is certain that they are in no way associated with the IMP), up to 30 days from the end of the study for each subject (which is usually the SFU visit), and to also inform participating subjects of the need to inform the Investigator of any SAE within this

period. Serious AEs that the Investigator thinks may be associated with the IMP must be reported to UCB regardless of the time between the event and the end of the study.

Upon receipt of the SAE report form, UCB will perform an assessment of expectedness of the reported SAE. The assessment of the expectedness of the SAE is based on the current version of the CZP Investigator's Brochure (IB).

12.2.3 Follow up of serious adverse events

An SAE should be followed until it has resolved, has a stable sequelae, the Investigator determines that it is no longer clinically significant, or the subject is lost to follow-up.

Information on SAEs obtained after clinical database lock will be captured through the PS database without limitation of time.

12.3 Adverse events of interest

An AE of interest is any AE which is listed in the European Risk Management Plan, or meets another commitment requiring nonstandard expedited reporting, even if the AE does not fulfill the expedited reporting criteria of "serious," "unexpected," and "associated with the use of the drug." Adverse events of interest include:

- Serious infections including opportunistic infections
- Malignancies including lymphoma
- Congestive heart failure
- Demyelinating-like disorders
- Aplastic anemia, pancytopenia, thrombocytopenia, neutropenia, and leucopenia
- Serious bleeding events
- Lupus and lupus-like illness
- Serious skin reactions (eg, Stevens Johnson Syndrome, toxic epidermal necrosis, and erythema multiforme)

12.4 Immediate reporting of adverse events

The following AEs must be reported immediately:

- SAE: AE that the Investigator classifies as serious by the above definitions regardless of causality
- Suspected transmission of an infectious agent via a medicinal product
- AE of interest (see [Section 12.3](#))

12.5 Anticipated serious adverse events

The following list of Anticipated SAEs has been identified, as these events are anticipated to occur in the population studied in this protocol at some frequency that is independent of drug exposure. This original list will remain in effect for the duration of the protocol.

This list does not change the Investigator's obligation to report all SAEs (including Anticipated SAEs) as detailed in [Section 12.2.2](#).

Table 12.1: Anticipated serious adverse events in population independent of drug exposure

Population	Anticipated SAE(s)
Rheumatoid arthritis ^a	Rheumatoid arthritis
Crohn's disease ^a	Crohn's disease Perianal abscess Abdominal pain
Ankylosing spondylitis	Ankylosing spondylitis
Psoriatic arthritis	Psoriatic arthritis
JIA	Juvenile arthritis

JIA=Juvenile Idiopathic Arthritis; SAE=serious adverse event; CD=Crohn's disease; RA=rheumatoid arthritis

^a The lists of anticipated SAEs were based on the treatment-emergent SAEs with an incidence $\geq 0.5\%$ in subject who participated in UCB sponsored placebo-controlled studies who received placebo (CD and RA safety pooling).

12.6 Laboratory measurements

Hematology, biochemistry, and urinalysis samples will be taken at Screening, Baseline (Week 0), Weeks 12, 24, 32, 36, 3 to 5 days prior to Week 48, and Weeks 60, 72, 84, 96/WD, and at the SFU Visit (10 weeks after the last dose). Testing for HLA-B27, hepatitis B surface antigen, and antibodies to hepatitis C and HIV will be performed at Screening. The urinalysis will be performed with a dipstick, and in case of a positive outcome, on a clean catch urine sample sent to the central laboratory for analysis. The central laboratory will analyze and assess blood and urine samples for the following:

Table 12.2: Laboratory measurements

Hematology	Chemistry	Urinalysis
Red blood cells	Sodium	pH
Hemoglobin	Potassium	Protein
Hematocrit	Chloride	Glucose
Platelets	Bicarbonate	Blood
White blood cells	Total calcium	Esterase
Neutrophils	Inorganic phosphorus	Microscopy (WBC, RBC, casts, crystals, bacteria) (Microscopy will be performed only when there are abnormalities on dipstick)
Lymphocytes	CRP	
Monocytes	Creatine phosphokinase	
Eosinophils	Glucose	Urine-sample to be collected for central-laboratory analysis only when there are abnormalities on dipstick
Basophils	Creatinine	
	Uric acid	
	Urea	
	Total protein	Others
	Albumin	Hepatitis B surface antigen
	Alkaline phosphatase	Antibodies to hepatitis C
	Aspartate aminotransferase	Antibodies to HIV
	Alanine aminotransferase	HLA-B27
	Bilirubin	Fecal calprotectin
	Total cholesterol	Serum calprotectin

CRP=C reactive protein; RBC=red blood cells; WBC=white blood cells; HIV=human immunodeficiency virus;
HLA=human leukocyte antigen

12.7 Other safety measurements

12.7.1 Pregnancy testing

Pregnancy testing must be carried out for women of childbearing potential and will consist of serum testing at Screening and SFU, and urine testing at Baseline and W96/WD.

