Abs=antibodies; ADAb= anti-CZP antibody; AEs=adverse events; AS=ankylosing spondylitis; AsQoL=Ankylosing Spondylitis Quality of Life; axSpA=axial spondyloarthritis; BASDAI=Bath Ankylosing Spondylitis Disease Activity Index; BASFI=Bath Ankylosing Spondylitis Functional Index; BASMI=Bath Ankylosing Spondylitis Metrology Index; CRP=C-reactive protein; CZP=certolizumab pegol; EQ-5D=EuroQoL Health Status Questionnaire; H=home, no site visit; HIV=human immunodeficiency virus; HLA-B27=human leukocyte antigen B27; HN=home nurse visit at subject's home; IBD=Inflammatory bowel disease; incl.=including; inj= injection; IXRS=Interactive Voice or Web Response System; MASES=Maastricht Ankylosis Spondylitis Enthesitis Score; MRI=magnetic resonance imaging; PE=physical exam; sc=subcutaneously; SF-36=Short-Form 36-item Health Survey; SFU=Safety Follow-Up; SI=sacroiliac; subj=subject; TB=tuberculosis; W=Week; WD=Withdrawal; WHO=World Health Organization

^a Assessments conducted 3 to 5 days prior to Week 48 will serve as the qualification assessments for subjects determined to be eligible for randomization into Part B at Week 48.

^b SFU: 10 weeks after last dose of study medication.

^c Informed consent: Prior to any study activities, subjects will be asked to read and sign the informed consent form for the conduct of the study. A separate informed consent form will be obtained from subjects consenting also to the use of their blood samples for possible genetic, genomic, and proteomic analysis.

^d Pulse rate, systolic and diastolic blood pressures, temperature, and respiration rate are to be measured at Screening and Baseline, thereafter pulse rate, systolic and diastolic blood pressures and temperature are to be measured. If a subject experiences an AE, respiration rate will be measured in addition.

^e Testing to rule out hepatitis B surface antigen, antibodies to hepatitis C, antibodies to HIV and HLA-B27 at Screening only.

^f To be assessed as indicated and from Week 52 onwards every 4 weeks only.

^g Pregnancy testing for women of childbearing potential will be serum testing at the Screening Visit and SFU and urine testing at Baseline and Week 96/WD Visit.

^h Includes evaluation of signs and symptoms of active TB and risk factors for exposure to TB. Weight is to be measured at Screening, Baseline, Week 48, and at Week 96/WD. Height will be measured at the Baseline Visit only.

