ⁱ Screening chest x-ray must have occurred within 3 months prior to Screening or during Screening, and should be repeated only if the TB test was confirmed positive or any further evidence is suggestive of potential TB infection (eg, exposure).

^j QuantiFERON TB GOLD test or another WHO-validated IGRA test such as Elispot test, if QuantiFERON TB GOLD test is not locally available. The TB test will be repeated at Week 48 and 96 (or at WD Visit if medically indicated) for subjects with previously negative TB test result.

^k Sacroiliac joint x-rays will be performed at Screening and used as the Baseline assessment for all subjects. An SIJ x-ray performed \leq 12 months prior to the Baseline Visit may be used as the Baseline assessment provided that the film can be submitted and meets the requirements for central reading.

^l Magnetic resonance imaging of the spine and sacroiliac joints to be performed at Screening, and within a \pm 2 weeks time window at Weeks 48 and 96 or WD Visit if the last MRI was performed more than 12 weeks prior to WD Visit.

^m Kit for collection of stool sample to be provided at Screening Visit. Stool sample shall be obtained prior to Baseline and provided to the Investigator at the Baseline Visit.

ⁿ Occiput to wall distance; chest expansion; and BASMI, which includes modified Schober test, lateral spinal flexion, cervical rotation, tragus to wall distance, and maximal intermalleolar distance.

^o Resource utilization includes: concomitant medical procedures, health care provider consultations not foreseen by the protocol, hospitalizations/emergency room visits.

^p Prior medication will be at Screening only.

^q Nurse visit at home only where approved and with agreement of subjects. Otherwise, the visit procedures will be done onsite by the site staff.

^r Refer to Protocol [Section 3](#) for definition. In case of loss of sustained remission in Part B, the subject must visit the study site for the next scheduled dose of study medication. The Investigator will initiate the escape treatment as appropriate. Refer to [Table 5.2](#) for details.

^s Subjects will be contacted by telephone about every 4 weeks in between the onsite visits.

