6 SELECTION AND WITHDRAWAL OF SUBJECTS

6.1 Inclusion criteria

To be eligible to participate in this study, all of the following criteria must be met:

1. An Institutional Review Board (IRB)/Independent Ethics Committee (IEC) approved written Informed Consent Form is signed and dated by the subject or by the parent(s) or legal representative.
2. Subject/legal representative is considered reliable and capable of adhering to the protocol (eg, able to understand and complete diaries), visit schedule, or medication intake according to the judgment of the Investigator.
3. Subject is at least 18 years old and not older than 45 years at the start of Screening Visit.
4. Female subjects must be either postmenopausal for at least 1 year, surgically incapable of childbearing, or effectively practicing an acceptable method of contraception (including oral/parenteral/implantable hormonal contraceptives, intrauterine device, or barrier and spermicide). Abstinence only is not an acceptable method. Subjects must agree to use adequate contraception during the study; and after the last dose of study treatment for at least 10 weeks (or - for participating countries of the European Union - 5 months in accordance with the Summary of Product Characteristics [SmPC]) or longer, if required by local regulations after the last dose of study treatment. Male subjects must agree to ensure that also their female partner(s) use adequate contraception during the study and for at least 10 weeks (or - for participating countries of the European Union - 5 months in accordance with the SmPC) or longer, if required by local regulations after the subject receives their last dose of study treatment.
5. Subjects must have a documented diagnosis of adult-onset axSpA with at least 3 months' symptom duration and meet the ASAS classification criteria for axSpA (according to Appendix 18.1) and symptom duration of less than 5 years prior to the participation of this study.
6. Subjects must have active disease at Screening as defined by

- ASDAS score ≥ 2.1
- BASDAI score ≥ 4
- Spinal pain ≥ 4 on a 0 to 10 NRS (from BASDAI Item 2)
- for mNY-negative subjects only: CRP $>$ upper limit of normal (ULN) and/or current evidence for sacroiliitis on the Screening MRI as defined by a ASAS/Outcome Measures in Rheumatology Clinical Trials (OMERACT) SI-MRI score ≥ 2 and confirmed by central reading

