RA=rheumatoid arthritis; SAARD=slow acting antirheumatic drug; SIJ=sacroiliac joint; SSZ=sulfasalazine

^a A table of corticosteroid equivalent doses is provided in Table 18.1 (Appendix 18.2)

^b Throughout the table, we refer to compounds such as sulfasalazine and methotrexate as SAARDs (slow-acting antirheumatic drugs). These medications are also commonly referred to as DMARDs, but since there is no evidence that they are in fact disease-modifying in axSpA (unlike in RA), we have opted for the more appropriate SAARD terminology.

Previous clinical studies and previous biological therapy exclusions

9. Subjects must not have received any nonbiological therapy for axSpA not listed above within or outside a clinical study in the 3 months or within 5 half-lives prior to the Baseline Visit (whichever is longer).
10. Subjects must not have received any experimental biological agents (defined as those agents unlicensed for use in axSpA in Europe or the USA).
11. Subjects must not have received previous treatment with a polyethylene glycolylated (PEGylated) compound that resulted in a severe hypersensitivity reaction or an anaphylactic reaction.
12. Subjects may not have been exposed to more than 1 TNF antagonist prior to the Baseline Visit and may not be a primary failure to TNF antagonist therapy (defined as no response within the first 12 weeks of treatment with the TNF antagonist).

Medical History Exclusions

13. Female subjects who are breastfeeding, pregnant, or plan to become pregnant during the study or within 10 weeks (or – for participating countries of the EU – 5 months in accordance with the SmPC) following the last dose of the investigational product.
14. Subjects with a history of chronic or recurrent infections (more than 3 episodes requiring antibiotics or antivirals during the preceding year), recent serious or life-threatening infection within the 6 months prior to the Baseline Visit (including hospitalization for any infection in the last 6 months or any current sign or symptom that may indicate an infection).
15. Subjects with a history of herpes zoster infection within 6 months prior to the Baseline Visit.
16. Subjects with known TB infection, at high risk of acquiring TB infection, or LTB infection are excluded.
 - a. Known TB infection whether present or past is defined as:
 - Active TB infection or clinical signs and symptoms suggestive of TB (pulmonary or extra pulmonary)

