8.3 Weeks 2 to 96/WD onsite visits

8.3.1 Weeks 2, 4, 12, 24, 32, 36, 48, 52, 60, 72, 84, and 96/WD (\pm 3 Days)

Assessments at these onsite visits include:

- Vital signs: pulse rate, systolic and diastolic blood pressures, temperature will be measured (all visits). If a subject experiences an AE, respiration rate will be measured in addition.
- Blood samples will be collected for hematology and biochemistry analyses (at Weeks 12, 24, 32, 36, 60, 72, 84, and at Week 96/WD), and CRP (at Weeks 2, 4, 12, 24, 32, 36, and from Week 52 onwards every 4 weeks only).
- Urine pregnancy testing for women of childbearing potential will be at Week 96/WD only.

- Urine will be collected for urinalysis (at Weeks 12, 24, 32, 36, 48, 60, 72, 84, and at Week 96/WD).
- Physical examination (at Weeks 12, 24, 36, 48, 60, 72, 84, and at Week 96/WD), including weight at Week 48 and at Week 96/WD.
- Extra-articular assessments (at Weeks 4, 12, 24, 36, 48, 52, 60, 72, 84, and at Week 96/WD).
- TB test (at Week 48 and at Week 96/WD only).
- TB questionnaire (at Weeks 12, 24, 36, 48, 60, 72, 84, and at Week 96/WD).
- MRI (at Week 48 and at Week 96/WD only).
- BASMI and spinal mobility (at Weeks 2, 4, 12, 24, 36, 48, 52, 60, 72, 84, and at Week 96/WD only).
- BASDAI (at Weeks 2, 4, 12, 24, 32, 36, 52, 60, 72, 84, and at Week 96/WD).
- BASFI (at Weeks 2, 4, 12, 24, 36, 60, 72, 84, and at Week 96/WD only).
- SF-36 (at Weeks 4, 12, 24, 36, 60, 72, 84, and at Week 96/WD only).
- ASQoL (at Weeks 2, 4, 12, 24, 36, 60, 72, 84, and at Week 96/WD only).
- EQ-5D (at Weeks 12, 24, 36, 60, 72, 84, and at Week 96/WD only).
- IBD-Q (at Week 96/WD only).
- MASES (at Weeks 12, 24, 36, 48, 60, 72, 84, and at Week 96/WD only).
- Total spinal pain NRS and nocturnal spinal pain NRS (at Weeks 2, 4, 12, 24, 36, 52, 60, 72, 84, and at Week 96/WD only).
- Swollen and tender joint counts (at Weeks 2, 4, 12, 24, 36, 48, 52, 60, 72, 84, and at Completion at Week 96/WD only).
- PtGADA (at Weeks 2, 4, 12, 24, 32, 36, and from Week 52 onwards every 4 weeks only).
- PhGADA (at Weeks 12, 24, 36, 48, 52, 60, 72, 84, and at Week 96/WD only).
- WPS (at Weeks 4, 12, 24, 36, 48, 60, 72, 84, and at Week 96/WD only).
- Resource utilization (at Weeks 12, 24, 36, 48, 60, 72, 84, and at Week 96/WD only).
- Plasma for CZP concentration and ADAb (at Weeks 4, 12, 24, 60, 72, 84, and at Week 96/WD only).
- Plasma for biomarkers (at Weeks 4, 12, 24, 60, 72, 84, and at Week 96/WD only), if applicable.

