12.1.2 Procedures for reporting and recording adverse events

The subject will be given the opportunity to report AEs spontaneously. A general prompt will also be given at each study visit to detect AEs. For example:

"Did you notice anything unusual about your health (since your last visit)?"

In addition, the Investigator should review any self-assessment procedures (eg, diary cards) employed in the study.

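### After Baseline no scheduled pregnancy test falls while doses remain; one urine test before randomisation at Week 48 would be a cheap safety improvement

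*Protocol*

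**What the plan says.** Section 12.7.1 sets four tests: "serum testing at Screening and SFU, and urine testing at Baseline and W96/WD". Table 5.1, footnote g, repeats this: testing "will be serum testing at the Screening Visit and SFU and urine testing at Baseline and Week 96/WD Visit". For the onsite visits from Week 2 on, Section 8.3.1 is explicit: "Urine pregnancy testing for women of childbearing potential will be at Week 96/WD only".

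The protocol clearly means to prevent exposure in pregnancy. Inclusion criterion 4 reads "Abstinence only is not an acceptable method. Subjects must agree to use adequate contraception during the study", and exclusion criterion 13 bars "Female subjects who are breastfeeding, pregnant, or plan to become pregnant during the study or within 10 weeks" of the last dose (5 months in EU countries). Withdrawal criterion 5 in Section 6.3.1 and the instructions in Section 12.1.6 require withdrawal, and an immediate stop of study drug, once pregnancy is shown by a positive test.

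There are indirect routes to detection. Section 12.1.2 says: "A general prompt will also be given at each study visit to detect AEs". Table 5.1, footnote s, adds: "Subjects will be contacted by telephone about every 4 weeks in between the onsite visits". Section 8.8 lists pregnancy testing among the assessments that may be done at an Unscheduled Visit, at the Investigator's discretion.

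**The concern.** Contraception can fail, and an early pregnancy may go unrecognised. The protocol's response rests on a positive test, yet between the first dose and the last its schedule never produces one. A woman who does not suspect a pregnancy could go on receiving study drug, including self-injections at home in Part A and during escape. She could also be randomised at Week 48 with no pregnancy test since Week 0. What is at stake is patient safety: whether the stop rule can operate in the case that self-report misses.

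**Working it through.** No sample-size, power or alpha figure is involved. The check sets the testing schedule against the dosing schedule.

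**Scheduled tests.** Serum at Screening (8.1), urine at Baseline before the first dose (8.2), urine at Week 96/WD (8.3.1), serum at SFU (8.6). Section 12.7.1 and Table 5.1, footnote g, agree.

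**Visit lists with no pregnancy test.** The visit 3 to 5 days before Week 48 (8.3.2), home visits in Part A (8.4.1), home and home-nurse visits in Part B (8.4.2), and the escape schedule (8.5 and Table 5.2).

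**Dosing.** Every 2 weeks from Week 0. Section 5.1.4 puts the last regular administration at Week 94, and Section 8.3.1 excludes dosing at Week 96/WD.

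**Gaps between scheduled tests.**
- Regular completer: Week 96 − Week 0 = 96 weeks. The later test comes 96 − 94 = 2 weeks after the last dose.
- Late escaper, using the example in 8.5 (Escape Week 0 at Week 84, last dose at Week 96, final visit at Week 98): 98 − 0 = 98 weeks, with the test 98 − 96 = 2 weeks after the last dose.
- Subject withdrawn early: the WD test follows the decision to stop treatment, so it cannot stop a dose either.

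**Rules against schedule.** Section 6.3.1, criterion 5, and Section 12.1.6 act on a positive test. Since no scheduled test lies between the first and last dose, a positive result in that interval can come only from a pregnancy that the woman suspects or reports, or from a test the Investigator chooses to do.

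**Where urine is already available.** Section 8.3.1 states: "Urine will be collected for urinalysis (at Weeks 12, 24, 32, 36, 48, 60, 72, 84, and at Week 96/WD". Section 8.5 collects urine at Escape Week 0 and every 12 weeks thereafter. The sources differ around Week 48: Section 12.6 and Table 5.1 place the sample 3 to 5 days before that visit, whereas 8.3.1 places it at Week 48.

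**Effect of added tests on a completer's longest gap.**
- One test at Week 48: 48 − 0 = 48 and 96 − 48 = 48, so 96 falls to 48 weeks (the earlier sample shifts this by 3 to 5 days).
- Tests at Weeks 12, 24, 36, 48, 60, 72 and 84: every interval, including 96 − 84, is 12 weeks. That is 7 added tests.

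**The case against.** The strongest reply is that the schedule is deliberate and layered. Women planning pregnancy are excluded and contraception is mandatory. Adverse events are prompted at study visits, a nurse or site staff give the dose every 2 weeks in Part B before any escape, and physical examinations are done at Weeks 12, 24, 36, 48, 60, 72 and 84. A test can be done at any Unscheduled Visit. Section 12.1.6 itself starts from the Investigator being notified of a pregnancy, which suggests intended reliance on notification followed by a confirmatory test. The protocol states no required testing interval, so none is breached.

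Much of this stands: nothing is misstated or contradictory, and any interval beyond a Week 48 test is a judgement. It does not close the gap, because prompts, contacts and examinations mainly catch a pregnancy that is already suspected or reported.

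A reader might also infer more than the documents support:
- *The number of doses given between tests measures harm.* It does not. The relevant quantity is doses between conception and recognition, which cannot be derived from the protocol.
- *Most women are affected because most Part A subjects are expected not to enter Part B.* Section 14.8 gives an assumption for all subjects; there is no split by sex.
- *The primary endpoint is at risk because withdrawal from Part B counts as a flare (14.3.1).* No pregnancy rate is given, and an isolated withdrawal is immaterial in arms of 70 with stated power of 98% and 94%.
- *Week 48 raises exposure.* These women are already on the full dose; it is a checkpoint, not a step up.

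**Conclusion.** The point holds as a cheap patient-safety improvement. From the first dose to the last, no pregnancy test is scheduled, on either the regular or the escape schedule, and a regular completer goes 96 weeks between scheduled tests. In that time the stop and withdrawal rules work only through self-report or a discretionary test.

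This rests on the current protocol text alone. The document does not show whether local requirements or consent forms add tests. It gives no number of women of childbearing potential, no pregnancy rate and no fetal-risk figure, so no expected number of exposed pregnancies is claimed. Sample size, power and type I error are unaffected.

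**What to change.** **Minimum.** Amend 12.7.1, 8.3.1/8.3.2 and Table 5.1 to add a urine pregnancy test for women of childbearing potential before randomisation at Week 48, read before dosing. State whether it uses the sample taken 3 to 5 days earlier (12.6) or the one at Week 48 (8.3.1).

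**Preferred.** A Week 48 test does not protect women during Part A or escape. Also test at onsite visits where urine is already collected, for example every 12 weeks, and at Escape Week 0 and every 12 weeks thereafter (8.5 and Table 5.2). This interval simply follows the existing visits.

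**Handling of results.** State in 6.3.1, criterion 5, and in 12.1.6 that study drug is held on a positive urine test and that the subject is withdrawn after serum confirmation, so that a false positive does not cost her place in the study.

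**Cost.** An amendment needing sponsor, IRB/IEC and, where required, regulatory approval (15.5) across about 95 sites (5.1.5), helping only women still on treatment when it takes effect. It adds one strip per woman at minimum, or seven for a completer at the 12-week interval. An occasional false positive will need serum confirmation and may delay a dose. No visit is added, since urine is already collected and onsite dosing already comes after the other assessments.
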